#### Risks with MRI

MRI does not involve ionizing radiation and it has been approved FDA for routine clinical use. In addition to the risks of static and time-varying magnetic fields and Specific Absorption Rate (SAR), which are minimal in our FDA-approved 3T system, there are three main potential risks to take into account.

Potential presence of metal objects. A safety risk is posed by the attraction of ferromagnetic metal objects by the high strength magnetic fields. The presence of a metal foreign object implanted in the subject is determined by interviewing each potential subject and completing a detailed screening questionnaire. Participants and staff are instructed to remove all metal objects, including clothing with metal clasps before entering the magnet room. The magnetic properties of unknown material are tested outside the magnet room with a strong permanent magnet. Participants and staff are also instructed to enter the magnet room slowly and pause at the entrance to determine if any items on their person may be pulling toward the magnet.

Potential discomfort due to confinement. The second concern is the discomfort some participants encounter by the confinement within the bore of the MRI system. Some participants may feel uncomfortable or confined once positioned within the bore of the MRI system. This potential reaction is reduced by discussing the procedure prior to entry into the magnet room, by providing the subject with a mirror through which they can look out into the room, and by communicating with the subject over the intercom. During set-up and anatomical imaging, participants can choose to listen to music or the radio over their headphones. Nevertheless, if participants

continue to feel uncomfortable, the imaging procedure is terminated, and the subject is removed from the magnet participation.

Potential risk of hearing loss from the MRI. The third concern is the loud noise made by the gradients during imaging. These risks occur for all clinical MRI exams and are not increased by the proposed research. Participants are required to wear earplugs during scanning to reduce noise levels below FDA limits. The sound levels within our scanners and have determined that they are compliant with FDA guidelines.

Incidental findings in MRI. MRI data obtained are for scientific research purposes only, and the investigators will not be looking for any existing brain abnormalities. The researchers that will be analyzing the MRI recordings are not medical specialists and cannot provide any medical interpretation of this data. If a possible abnormality is incidentally observed in either the MRI data that a researcher believes might be of concern, a physician associated with Duke Hospital may be contacted to look at the data. If they conclude that additional testing is medically indicated, the participant will be informed of this so that he or she can consider pursuing any follow-up courses of action.

Other plausible risks include breach of confidentiality, development of suicidal thoughts and syncope (neurocardiogenic in nature). Vasodepressor (neurocardiogenic) syncope is a common reaction to anxiety and psycho-physical discomfort. It is a common experience that may occur more often than epileptic seizures during TMS testing and treatment. Suicidal thoughts have been observed to transiently develop only in subjects who have a previous history of major depressive disorder.

The study proper may benefit subjects in decreasing alcohol use. It will also help us learn how TMS affects cognitive functions, visual attention, craving and impulsivity in people with alcohol use disorder. There are no known long-term health risks to the use of rTMS per se when operated within consensus safety guidelines (Rossi 2009). In 2008, the FDA approved the use of high frequency rTMS in the treatment of depression. Also in 2008, an international consensus conference on safety guidelines for rTMS (1) systematically reviewed the thousands of healthy subjects and patients who have undergone rTMS in order to allow for a better assessment of relative risks. The relative infrequency of adverse events using rTMS was noted. They concluded that in the case of Class 3 studies (studies involving indirect benefit and low risk in normal subjects and patients that are expected to yield important data on brain physiology or safety, but have no immediate relevance to clinical problems), normal volunteers should be permitted to participate in rTMS research when it is likely to produce data that are of outstanding scientific or clinical value. They also concluded that this research can be performed in a non-medical setting (i.e., psychology labs, robotics labs, research institutions, etc. as opposed to a hospital or appropriately equipped outpatient clinic). The Rossi et al. consensus report went on to suggest safety guidelines based on the now rather extensive international experience with rTMS. These guidelines include the rTMS intensity and timing parameters considered safe, training, and planning for and managing emergencies. We will follow these guidelines, and have incorporated them into our screening and session procedures.

Participation in the study is completely voluntary, and there will be no pressure or time constraints regarding the decision to participate. If subjects experience headaches, they can withdraw without any ramifications pertaining to their respective clinic. There are no benefits to the participants except for the compensation, as well as the good will of helping the progress of scientific research. The information learned from this study may aid our understanding of the role of the TMS in modulating cognition and brain function in patients with alcohol use disorder.

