**Research Procedures**

Describe how the research will be conducted.

- What experience will study participants have?
- What will study participants be expected to do?
- How long will the study last?
- Outline the schedule and timing of study procedures.
- Provide visit-by-visit listing of all procedures that will take place.
- Identify all procedures that will be carried out with each group of participants.
- Describe deception and debrief procedures if deception is involved.

Differentiate between procedures that involve standard/routine clinical care and those that will be performed specifically for this research project. List medications that are explicitly forbidden or permitted during study participation.

On day one of the study, following informed consent, we will perform baseline assessments including breath alcohol level, alcohol craving questionnaire, alcohol attentional bias tasks using eye tracker, and collection of baseline demographics. All of these baseline assessments will take a total of three hours. We will evaluate for any contraindications for MRI using the MRI checklist (attached). We will also obtain resting and active motor threshold from the first dorsal interosseous (FDI) muscle. Following this subjects will be transported to Magnetic Resonance Imaging and Spectroscopy Center (MRISC), affiliated with University of Kentucky for collection of their baseline MRI brain scan that will last thirty minutes. A study team member will escort them to the MRISC and will be with them when the scan is obtained.

On the second day, subjects will receive two sessions of active cTBS. Sessions will be the same in dosing and will be delivered at an interval of fifty minutes. Each session will last five minutes regardless of it being cTBS or sham cTBS. Active cTBS sessions will be delivered 120% resting motor threshold (RMT) to the left dorsolateral prefrontal cortex using a figure 8 coil and MagVenture MagPro x100 device (MagVenture A/S, Denmark), with TMS coil position stabilized using BrainSight (Rogue Solutions, Montreal, Canada). Subjects will also perform a host of other tasks as shown in figure 1 before and after the two cTBS sessions. At the end of the cTBS sessions and tasks, post session MRI brain scan will be collected at MRISC.

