On day three of the study, participants will receive two sessions of sham cTBS. The sham cTBS mimics the actual experimental one but does not deliver any electricity to the brain. The sham sessions will be separated by 50 minutes. Participants will perform a host of other tasks as shown in figure 1 before and after the two sham cTBS sessions. At the end of day three, we will have participants undergo an MRI brain scan at MRISC.

A medical doctor will be present or nearby during all stimulation sessions. No drug, pregnancy, etc. screening results will be obtained from a UK HealthCare laboratory.

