#### Data and Safety Monitoring

The IRB requires review and approval of data and safety monitoring plans for greater than minimal risk research or NIH-funded/FDA-regulated clinical investigations.

- If you are conducting greater than minimal risk research, or your clinical investigation is NIH-funded, describe your Data and Safety Monitoring Plan (DSMP). [Click here for additional guidance on developing a Data and Safety Monitoring Plan](#).
- If this is a non-sponsored investigator-initiated protocol considered greater than minimal risk research, and if you are planning on using a Data and Safety Monitoring Board (DSMB) as part of your DSMP, [click here for additional guidance](#) for information to include with your IRB application.

We will monitor the safety of participants, i.e., potential adverse events resulting from participation; and have procedures to safeguard against adverse events. We will actively screen and exclude any potential participants with a history of seizure disorder. We will also monitor every study session with a physician on site for every stimulation session. In case a seizure were to occur, having a physician on site in the room with the participant will help us in managing the event. All staff will also be trained in how to provide first aid in the event of a seizure ie lay the participant on their side and move any objects that can cause harm out of their vicinity.

We will also monitor for side effects after every stimulation session including headaches and neck pain. We will actively exclude participants with metal implants or piercings so that no adverse events occur during the MRI scan.

We will assure data accuracy and protocol compliance, including quality-control procedures in place to assure data accuracy and completeness. Appropriate procedures range, for example, from regular data verification and protocol compliance checks performed by a data manager and a principal investigator, to a formal external data audit process by an external agent.

[Back to Top](#)

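### The only visible rule for a possible abnormality on a study MRI makes medical review optional and assigns it to a hospital with no described role in the study

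*Combined protocol and SAP*

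**What the plan says.** The paragraph on incidental findings, under Risks with MRI in Potential Risks & Benefits, explains that the scans are for research and that nobody will be searching them for brain abnormalities. On who looks at the images it says: "The researchers that will be analyzing the MRI recordings are not medical specialists and cannot provide any medical interpretation of this data". If a researcher nevertheless notices something that might matter, "a physician associated with Duke Hospital may be contacted to look at the data". It then states the consequence: "If they conclude that additional testing is medically indicated, the participant will be informed of this".

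Scanning takes place at the University of Kentucky imaging centre. Study Design places the baseline scan there. Research Procedures does the same for the active day ("post session MRI brain scan will be collected at MRISC") and the sham day ("At the end of day three, we will have participants undergo an MRI brain scan at MRISC").

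Medical cover is described for stimulation. Research Procedures says "A medical doctor will be present or nearby during all stimulation sessions", and Data and Safety Monitoring says "We will also monitor every study session with a physician on site for every stimulation session". The only MRI item in that monitoring answer concerns eligibility: "We will actively exclude participants with metal implants or piercings so that no adverse events occur during the MRI scan".

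**The concern.** Two things in the incidental-findings paragraph do not fit the rest of the study. The first is the verb: *may* creates no duty, although the person deciding is by the protocol's own account not medically qualified to judge what was seen. The second is the reader: the physician is identified by a hospital that plays no other part in the visible plan, so a researcher following the text would not know whom to call.

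At stake is one participant's chance of learning about a finding that needs follow-up. It is a safety and process matter and does not bear on validity or estimation.

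**Working it through.** The plan gives no figure here that could be reproduced. The check is a reading of the text, plus a count of the people concerned.

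**Step 1: follow the rule in order.**

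| Step | What the text provides | Firm or optional |
|---|---|---|
| Trigger | A researcher without medical training believes that something on the scan might be of concern | Depends on that person's judgement |
| Medical look | A physician associated with Duke Hospital | Optional |
| Medical conclusion | That physician decides whether testing is indicated | Arises only if the physician was contacted |
| Telling the participant | Participant is informed | Firm, but conditional on the step above |

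The one firm commitment comes last and is reached only through the optional step.

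**Step 2: compare the named reader with the rest of the protocol.**
- Study Population and the recruitment section draw participants from University of Kentucky clinics.
- Resources puts the stimulation suite in that university's psychiatry department.
- Study Design, Research Procedures, and Data Collection & Research Materials put the scans at that university's imaging centre.
- In Research Sites, no entry is visible at the free-text prompts for outside locations and outside roles. The checkbox states cannot be read, so they are not relied on.
- Duke Hospital is named once in the visible text, in this paragraph.

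**Step 3: look for another route for a flagged scan.**
- The MRI checklist in Research Procedures, and the metal, confinement and noise paragraphs under Risks with MRI, deal with matters before or during scanning.
- The monitoring answer covers exclusion for metal.
- The physician in Research Procedures and Data and Safety Monitoring is tied to stimulation sessions.
- The medical screener in the recruitment section is tied to eligibility.
- Records, Privacy, and Confidentiality mentions incidental findings only as a link in the form's instructions.

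No visible text assigns a flagged scan to anyone else.

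**Step 4: size.** Subject Info To-Date gives 4 previously reported + 4 new = 8 enrolled. The completed demographics table agrees: 4 + 3 + 1 = 8. With one scan on each of three study days, the ceiling is 3 × 8 = 24 scans, if everyone completed every visit. The documents give no rate of incidental findings, so no expected number is offered.

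**Step 5: effect on the analysis.** The SAP compares changes in craving scores and attentional bias by t-tests and names no MRI outcome. Nothing in it depends on this paragraph.

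**The case against.** The strongest reply is that the pages where a firmer rule would naturally sit are not available. Consent and personnel pages were removed, and attachments are only listed. The form also links to institutional guidance on incidental findings. This stands as a limit: a named reviewer may exist elsewhere. It does not make the current paragraph right, because that paragraph would still need to agree with the other document.

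A second reply is that the hospital name is a drafting slip and that *may* is ordinary wording in a risk description. Either could be so. The paragraph also does not forbid asking another physician. But the permissive verb would be easier to pass over if the named reader belonged to the study or a second route were described, and neither is visible.

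A third reply is that little is at stake now. Progress of the Research says that the study is closing and only data analysis remains, and the SAP does not confirm that MRI analysis is among that work. This stands and is the reason for treating the point as minor.

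A reader might also infer more than the text allows:
- **That a finding was missed or ignored.** No flagged scan or harm is documented, so there is no ground for a retrospective check.
- **That the paragraph was carried over from another institution.** This is plausible, but the documents do not say so.
- **That data-sharing or site rules were broken.** Nothing shows that any scan was sent outside.
- **That every scan needs a clinical read.** The point concerns only scans that a researcher already thinks might be of concern.

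**Conclusion.** The point holds as a minor participant-safety correction. As written, the only visible rule for a possible abnormality makes the medical look discretionary and gives it to a physician with no described link to the study. The promise to inform the participant depends on that step. The conclusion assumes that the visible text is the operative rule; a provision in the unavailable pages would narrow the problem to an inconsistency between documents. The reach is at most 8 enrolled people. Confidence is medium, because of the unavailable pages. The stronger claim that the study has no arrangement at all for incidental findings is not supported.

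**What to change.** In the incidental-findings paragraph under Risks with MRI:

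1. Replace the Duke Hospital reference with a University of Kentucky physician or a physician already in the study. If the outside reader is intended, describe that role instead. Either way, match any reviewer named in the consent form.
2. Change *may* to *will*, so that contact is required for any scan that a researcher believes might be of concern.

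The cost is a short text change and a little physician time if a scan is flagged. It needs no new scans, visits or staff, and no change to the SAP.

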**Study Population:**

Describe the characteristics of the subject population, including age range, gender, ethnic background and health status. Identify the criteria for inclusion and exclusion.

Provide the following information:

- A description of the subject selection criteria and rationale for selection in terms of the scientific objectives and proposed study design;
- A compelling rationale for proposed exclusion of any sex/gender or racial/ethnic group;
- Justification for the inclusion of vulnerable groups such as children, prisoners, adults with impaired consent capacity, or others who may be vulnerable to coercion or undue influence.

Please consider these resources:

[NIH Diversity Policy](#)

[FDA Diversity Guidance](#) 

Inclusion criteria. Potential participants will be: 1) Patients seen at a clinic within the University of Kentucky Healthcare; 2) 21-60 years of age; 3) male or female gender 4) Able to read, understand and communicate in English; 5) willing to adhere to the general rules of the UK Healthcare; 6) Must fulfill DSM criteria for moderate alcohol use disorder.

Exclusion criteria. Positive pregnancy test for females, traumatic brain injury, history of seizure disorder, history of or current diagnosis of schizophrenia, intracranial metal shrapnel, previous adverse effect with TMS, sub-threshold consistency while performing behavioral tasks, failure to show baseline attentional bias to alcohol versus neutral cues.

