#### Risks with TMS

Seizure is a theoretical risk with TMS. In the Rossi et al. report it was stated that "The occurrence of seizures has been extremely rare, with most of the few new cases receiving rTMS protocols exceeding previous guidelines, often in patients under treatment with drugs which potentially lowered the seizure threshold." As Rossi et al. delineate, "rare" means that 16 cases (out of tens of thousands of rTMS sessions over the last two decades) of seizure related to rTMS have been reported. Eight occurred before safety parameters were established in 1997. Of the other eight reports, six occurred either when the safe rTMS parameters were exceeded or other safety guidelines ignored, and the actual occurrence of a seizure has been questioned in the other two (i.e., convulsive syncope or pseudoseizure may have occurred). In a workshop convened by the National Institute for Neurological Disorders and Stroke (NINDS) in 1996, researchers in the field agreed upon a set of rTMS consensus safety guidelines, including recommended stimulation parameters and contra-indications, and these consensus guidelines have been recently updated (Rossi et al., 2009). Widespread adherence to the 1996 guidelines has resulted in the virtual elimination of inadvertent seizures in rTMS studies (Rossi et al., 2009). Theta burst stimulation (TBS) that we will use in this study has been documented to be extremely safe. The risk of seizure with TBS is 0.1% (Rachid, 2017). There has been only one seizure instance reported with continuous TBS in a subject with no previous history of epilepsy but was sleep deprived after a long flight (Oberman and Pascual-Leone, 2009).

The most commonly reported side effect of rTMS is headache. This headache is typically of a muscle-tension type. It usually develops during or immediately after the stimulation and may last for minutes to hours following the end of the stimulation. It is typically limited to the day of stimulation, and usually responds promptly to single doses of over the counter pain medications. Neck pain or scalp pain may also occur. Both are usually managed easily with over-the-counter analgesics.

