As noted in Rossi et al. (2009), Loo and colleagues reported mild and transient changes in auditory threshold in two depressed patients following a 2-4 week rTMS course of rTMS (16). Cases of tinnitus have been reported after rTMS treatments. In addition, recently in a study investigating the effects of rTMS on symptoms of depression, a patient experienced moderate to severe tinnitus after an rTMS session in which earplugs were not used. Rossi et al. recommended that hearing protection always should be worn during rTMS application, and that individuals with cochlear implants not receive rTMS. In the current study, earplugs will be worn by all subjects during rTMS procedures. Individuals with cochlear implants will be excluded from participation.

Risks to the unborn children of pregnant women receiving rTMS are unknown. Pregnant women will be excluded in this study. If sexually active, the subject must agree to use appropriate contraceptive measures for the duration of the study. Medically acceptable contraceptives include: (1) surgical sterilization (such as a tubal ligation or hysterectomy), (2) approved hormonal contraceptives (such as birth control pills, patches, implants or injections), (3) barrier methods (such as a condom or diaphragm) used with spermicide, or (4) an intrauterine device (IUD). Contraceptive measures such as Plan B (TM), sold for emergency use after unprotected sex, are not acceptable methods for routine use. If the subject has any uncertainty about whether they could be pregnant, another urine pregnancy test will be performed before they can participate in this protocol.

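### Suicidal thoughts are a named risk, but no stated check asks about them, and no question covers the week between active and sham stimulation

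*Combined protocol and SAP*

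**What the plan says.** The risk text under Risks with MRI lists suicidal thoughts among other plausible risks and says who is affected: "Suicidal thoughts have been observed to transiently develop only in subjects who have a previous history of major depressive disorder". The exclusions under Study Population include "history of or current diagnosis of schizophrenia, intracranial metal shrapnel, previous adverse effect with TMS", but no history of major depression. Records, Privacy, and Confidentiality says that psychiatric comorbidity is stored, without linking it to any safety question.

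Risks with TMS also covers hearing ("Cases of tinnitus have been reported after rTMS treatments") and headache.

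On ascertainment, Data and Safety Monitoring says: "We will also monitor for side effects after every stimulation session including headaches and neck pain". No other timing for side-effect questions is given. Data Collection & Research Materials lists a TMS side-effects scale without a schedule, and lists no mood, suicidality or hearing measure.

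On sequence, Study Design gives active stimulation to everyone first (Day 2) and sham to everyone a week later (Day 3). Research Procedures ends with a scan: "At the end of day three, we will have participants undergo an MRI brain scan at MRISC". The only later step described is a mailed payment.

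**The concern.** The protocol identifies a serious psychiatric risk and the group who carry it, leaves that group eligible, and then describes no question that would detect it. The stated check is tied to the end of each session. The week after the only active exposure is not covered by any stated contact, or by any stated question when participants return.

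Two things are at stake. The first is detection: an event in that week enters the data only if the participant volunteers it, because Subject Recruitment Methods & Advertising rules out any use of medical records. The second is attribution: the order is the same for everyone, so an effect of active stimulation that is first mentioned at a post-sham check on Day 3 would sit in the record as a sham-day event, with nothing to separate the two. Earlier experience with this regimen is not available as a substitute. The Background says that no previous study gave several cTBS sessions in one day or applied cTBS to this target.

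**Working it through.** No sample-size or power figure is in dispute and the plan gives no figure to reproduce. The check sets the visit timeline against the named risks.

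**Timeline, from Study Design, Research Procedures and Data and Safety Monitoring**

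| Point | Exposure | Stated side-effect check |
|---|---|---|
| Day 1 | none (baseline tests, motor threshold, scan) | none stated |
| Day 2 | 2 active sessions, 50 minutes apart, then tasks and scan | after each session: 2 |
| The week between | none | no contact stated: 0 |
| Day 3, before sham | none | no question about the week stated: 0 |
| Day 3 | 2 sham sessions, then tasks and scan | after each session: 2 |
| After Day 3 | none | no contact stated: 0 |

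Stated checks per participant: 2 + 2 = 4, all straight after a session. The interval from the last active session to the next contact is about 7 days.

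**Named risks against those checks**

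- *Suicidal thoughts.* No item is named in the monitoring text or the data list, so 0 of the 4 checks are stated to cover them. The protocol calls them transient and gives no time of onset. Thoughts that came and went within the week would leave no trace in a check that asks only about the session just finished.
- *Hearing and tinnitus.* No item is named: again 0 of 4. The supporting cases are weaker for this design. The threshold changes were in two patients after a course of 2 to 4 weeks, and the tinnitus case described in detail involved a session without earplugs. This study gives two active sessions on one day, with earplugs for everyone.
- *Headache.* This is covered. It is named in the monitoring text, and the protocol says of its onset: "It usually develops during or immediately after the stimulation and may last for minutes to hours following the end of the stimulation". It adds: "It is typically limited to the day of stimulation". The post-session check is well timed for it; at most its duration could go unrecorded.

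**Attribution.** With order fixed as active then sham, every event that begins after Day 2 and is first elicited on Day 3 has two candidate sources. A question asked before sham would date it to the interval. No such question is stated, so a post-sham answer cannot be assigned to one or the other.

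**The case against.** The strongest reply is that most of the alarming version of this point is not in the documents.

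- A reader might infer that the main gap is the absence of contact after Day 3. Day 3 is sham and, by the protocol's own account, passes no current to the brain. Participants are seen in person about 7 days after the only active exposure, so follow-up after active treatment is not zero. This stands.
- A reader might infer that headache lasting hours goes undetected. The onset text quoted above contradicts that. This stands.
- A reader might infer that observation lasts only minutes. No duration is given, and participants stay for the second session, the tasks and the scan. This stands.
- A reader might infer that suicidal thoughts cannot be detected or would certainly be missed. The side-effects form and Figure 1 are not visible, the wording of the monitoring sentence makes headache and neck pain examples and not a full list, and participants may report events unprompted. So the supportable wording is that events could be missed. This stands.
- The statistical analysis plan makes no safety comparison between sessions, so misattribution to sham is a possibility in descriptive reporting and not a planned result. That limits the consequence but does not remove it, because side effects are collected by session day.
- Psychiatric history is already stored, so a new field for depression history may be unnecessary. That is fair.

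What the reply does not meet is the narrow point. The text names the risk and the people who carry it, specifies no question about it, and specifies no question about the week after active stimulation. The Day 3 visit closes that gap only if someone asks.

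**Conclusion.** The concern holds in a limited form. The risk text and the monitoring text do not match: suicidal thoughts are named in the first, and no item for them is specified in the second or in the data list, although past major depression is not a listed exclusion. The gap that matters is the week between active Day 2 and sham Day 3. Events in that week could be missed, or could first be recorded after sham and read as sham effects.

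Size: 4 stated checks per participant, 0 stated to cover suicidal thoughts, 0 stated to cover the roughly 7-day interval. Hearing is a secondary example, and headache is not a valid one. The documents do not support a conclusion that events were missed, or that the lack of contact after the sham day is the central fault.

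This rests on two assumptions that the sponsor can check at once: that the side-effects form has no suicidality item, and that neither the form nor Figure 1 sets a recall period or a pre-sham administration on Day 3. If either proves false, that part of the point falls away.

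**What to change.** **In the plan, if enrolment reopens or the design is reused.** Reconcile the risk text with Data and Safety Monitoring and the data list:

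1. Add suicidal thoughts to the existing TMS side-effects form, and hearing or tinnitus if not already there, with a baseline on Day 1.
2. Give the same form at the start of Day 3, before sham, with a recall period running from Day 2. Record those answers separately from the post-sham answers, without assigning cause in advance.
3. State the sponsor's own pathway for handling a positive answer. This review does not propose one.

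Cost: a few form items and two extra completions per participant (Day 1 and pre-sham Day 3), that is 2 × 30 = 60 at the planned enrolment. The downside is a slightly higher count of minor events.

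**In the report of this study.** The continuing-review sections record 8 participants and say that the study is closing with only data analysis left, so the missing questions cannot now be asked. The report should state what the form asked and when, limit any statement of no events to those items and that window, and say that the attribution of events first recorded on Day 3 is uncertain. This costs a few sentences.
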